## METHODS

The study was approved by the Institutional Review Board at the University of Washington (STUDY00006670). Participants and their parents/legal guardian were recruited from a pool of patients who were scheduled to receive comprehensive dental care under general anesthesia (GA) at the University of Washington Center for Pediatric Dentistry. Families were approached regarding study participation the day of the initial dental surgery consultation or were contacted by phone at least 2 days prior to their scheduled dental surgery appointment. Consent was obtained the day of the surgery. Inclusion criteria included American Academy of Anesthesiologists physical status classification (ASA) I or II, English speaking, and having caries lesions requiring prefabricated crowns on both primary maxillary first molars, teeth #B and I.

Subjects were excluded from the study if the parents or guardians were not able to communicate with the study coordinator in English or the patient had severe systemic illness (ASA III or greater), cardiac arrhythmia, cardiovascular disease, diabetes, thyroid disease and/or prescribed anti-arrhythmic, antihypertensive, or ionotropic medications. Subjects were also excluded if they required pulpotomy or pulpectomy treatment on the primary maxillary first molars.

This was a single blinded, split-mouth randomized controlled pilot study. We recruited patients from June 2019 until November 2019. Sixteen children met inclusion criteria and were approached for participation. Three patients were excluded from the study: One patient did not meet the inclusion criteria after new radiographs were taken under GA and two caregivers declined to participate in the study on the day of surgery (Figure 1).

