Randomization was performed in two stages. Using Stata 14.2 (StataCorp, College Station, TX) statistical software we first randomized whether the control treatment would be applied to the primary right or left maxillary first molar. The first randomization resulted in assignment of the right side of the mouth for the control treatment. This assignment was maintained for all participants. The second randomization step determined the treatment sequence; whether control or intervention treatment was done first. A randomization list was created and placed into a password protected Excel file prior to the start of the study. The order in which the patient received the intervention (either first or second) was randomly assigned to each patient using the randomization list.

The main objective of this method was to have each patient serve as their own control and ensure randomization of the timing (first or second) of the experimental condition. Parents were not present during the procedure, and patients were unconscious and therefore blinded to the intervention. The treating dentist and study personnel were not blinded.

Each patient's weight and medical history was updated on the day of surgery. All patients fasted for at least eight hours prior to the procedure. They were transferred to the operating room and received mask inhalation induction (8% sevoflurane and 50-70% N2O/O2). Monitoring

equipment was applied after the patient was anesthetized, and it was maintained in place throughout the course of the procedure. Vital sign measurements included capnography, oxygensaturated hemoglobin percentage (SpO2), heart rate (HR) in beats per minute (bpm), and cardiac rhythm-which was continuously recorded from a 5-lead electrocardiogram (ECG). The systolic blood pressures (SBP) and diastolic blood pressures (DBP) were measured in millimeters of mercury (mmHg) via standard automatic noninvasive arterial cuff on the ankle or upper arm.

All baseline vitals were recorded and peripheral intravenous (IV) access was obtained. Patients then received 1 to 2mg/kg of propofol, Decadron 4 to 6mg total and 0.5 mg/kg of ketorolac via IV, followed by direct laryngoscopy and nasotracheal intubation. Anesthesia was maintained throughout the procedure with a continuous IV infusion of propofol (50-100 mcg/kg/min), Remifentanil infusion (0.05-0.1 mcg/kg/min), and inhaled nitrous oxide/oxygen (30-70%).

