After successful intubation, necessary radiographs were taken, a throat pack was placed, followed by cleaning, dental examination and treatment planning. Next, the maxillary first primary molar that was randomized to be completed first was prepared to receive a zirconia crown. To reduce pressure stimulation, no dental isolation (e.g. rubber dam) was used during any of the study procedures. After preparation, an appropriately sized zirconia crown was fit, and baseline heart rate and blood pressure were recorded. Next, two saline or intervention pellets were stretched and applied directly around the gingival tissue of the prepared tooth covering the tooth circumference. Control pellets were prepared by soaking in 0.9% sodium chloride (physiological saline) whereas intervention pellets were obtained directly from the manufacturer, containing an average of 0.55 mg (0.42 to 0.68 mg/pellet) of racemic epinephrine hydrochloride per pellet (HemeRx, Racellet#3, Sprig Oral Health Technologies, Inc. Loomis, CA). Pellets were maintained in position for one

minute with gauze pressure based on manufacturer's recommendation. After pellet removal, any residual coagulum was removed using suction or moistened gauze.

Cardiovascular outcomes including patient's systolic blood pressure (SBP), diastolic blood pressure (DBP) and heart rate (HR) and mean arterial pressure (MAP) were recorded via standard automatic noninvasive arterial cuff immediately before pellet placement (baseline) and again at 1, 2, 3, 4 and 5 minutes after placement.

The adequacy of hemostasis was determined subjectively by the operating dentist/principal investigator ([name]), as "adequate" or "inadequate" at baseline and again at 1, 2, 3, 4 and 5 minutes after placement. Adequate hemostasis was defined as cessation of blood flow from gingival tissue. Inadequate hemostasis was defined as continued blow flow from gingival tissue, with blood contamination of the prepared tooth. Figures 2 and 3 demonstrate examples of adequate vs. inadequate hemostasis. Figure 4 demonstrates pre and post-op intraoral photos of maxillary arch of one of the patients.

Following study procedures, the remainder of each patient's dental care was completed, including application of rubber dam isolation, sealants, composite restorations, pulpotomies, stainless-steel crowns and extractions. All patients were discharged on the same day after adequate recovery and observation time.

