Data was analyzed using Stata SE version 14.2 (College Station, TX) software. Descriptive statistics are reported as mean and standard deviation. Paired t-test and one-way repeated analysis of variance (ANOVA) were used for comparison of cardiovascular outcomes within controls (Table 1) and within interventions (Table 2). A paired t-test with equal variance was used for comparing control and intervention cardiovascular values as well as time to hemostasis adequacy (Table 3). McNemar's Exact test was used to compare whether a patient reached adequate

hemostasis in the intervention and control sides. A p-value < 0.05 was considered to be statistically significant.

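### Treatment order is randomized for each child but no planned analysis uses it; the epinephrine-saline cardiovascular comparison should be adjusted for sequence

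*Combined protocol and SAP*

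**What the plan says.** METHODS describes two randomization steps. The first placed the control on the right side, and "This assignment was maintained for all participants". The second varied between children: "The second randomization step determined the treatment sequence; whether control or intervention treatment was done first". METHODS then confirms that this was done child by child: "The order in which the patient received the intervention (either first or second) was randomly assigned to each patient using the randomization list". Sequence is therefore the only factor randomized from child to child. On how the list was made, the text says "A randomization list was created and placed into a password protected Excel file prior to the start of the study". It mentions no blocking and does not report how many children fell in each sequence.

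For each tooth the cardiovascular readings were taken "immediately before pellet placement (baseline) and again at 1, 2, 3, 4 and 5 minutes after placement". METHODS gives no interval between the two teeth and no check that readings had returned to their starting level.

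The analysis paragraph at the end of METHODS says "A paired t-test with equal variance was used for comparing control and intervention cardiovascular values". It does not say whether these values are raw readings or changes from the tooth's own baseline. The other methods listed are paired t-tests and one-way repeated-measures ANOVA within each condition, a paired t-test for time to hemostasis, and McNemar's exact test. None has a term for order, period or sequence.

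**The concern.** The two teeth are separate sites for bleeding, but not for heart rate and blood pressure. For the primary outcomes each child is observed in two successive periods of one anesthetic, and the treatment given in each period is set by the randomized sequence. Readings can move between periods for reasons unrelated to the pellets, such as depth of anesthesia or elapsed time. In a paired analysis that ignores sequence, such a shift enters with one sign in epinephrine-first children and the opposite sign in saline-first children. It widens the spread of the differences, and with unequal sequences it also moves their mean.

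The stake is the safety conclusion. The INTRODUCTION hypothesizes no significant cardiovascular change relative to placebo, so a comparison that loses sensitivity makes that result easier to reach. With a lopsided split the same omission can instead produce a spurious difference.

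**Working it through.** **Inputs.** "Sixteen children met inclusion criteria and were approached for participation" and "Three patients were excluded from the study", so n = 16 − 3 = 13 pairs. The significance level is 0.05 (METHODS), taken as two-sided. The text gives no SD, effect size, power, drift or sequence split, so there is no figure of the plan's to reproduce. Below, everything is in units of the SD of the within-child difference, and 7:6 is the assumed split unless stated.

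**Model.** Let D be epinephrine minus saline, τ the treatment effect and π the period effect (second tooth minus first). Then D = τ − π + error in the n1 epinephrine-first children and D = τ + π + error in the n2 saline-first children.

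**Planned paired t-test (12 df).**
- Its mean is τ − π(n1 − n2)/13. At 7:6 the bias is 0.077π.
- Its expected variance is 1 + π²S/12, with S = 13 − (n1 − n2)²/13. At 7:6, S = 12.92. For π = 1 the variance is 2.08 and the SD 1.44.

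**Sequence-adjusted analysis (11 df).** The estimate is the average of the two sequence means, which is τ whatever π is. Its standard error is 0.5√(1/n1 + 1/n2), or 0.278 at 7:6, against 1/√13 = 0.277 for the planned test with no drift.

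**Interval width at 7:6, π = 1.** Planned half-width: 2.179 × 1.441 × 0.277 = 0.871. Adjusted: 2.201 × 0.278 = 0.612. The ratio is 1.42. It is 1.11 at π = 0.5, 1.02 at 0.25 and 0.99 at 0.

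**Power at 7:6.** The planned test has 80% power for τ = 0.85 with no drift. By simulation (favorable means the small bias pushes the estimate away from zero):

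| Size of π | Planned, favorable sign | Planned, unfavorable sign | Adjusted | Planned, rejection when τ = 0 |
|---|---|---|---|---|
| 0 | 80% | 80% | 79% | 5.0% |
| 0.25 | 80% | 76% | 79% | 4.4% |
| 0.5 | 76% | 68% | 79% | 3.1% |
| 1 | 58–59% | 39% | 79% | 0.8% |

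The sign depends on the direction of drift and on which sequence is larger. The text fixes neither.

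**Other splits.**

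| Split | Bias of planned mean | Adjusted power, π = 0 | Points lost against 80% | π at which interval widths are equal | Planned type I error, π = 1 |
|---|---|---|---|---|---|
| 7:6 | 0.08π | 79% | 1 | 0.16 | 0.8% |
| 8:5 | 0.23π | 77% | 3 | 0.28 | 2.5% |
| 9:4 | 0.38π | 73% | 7 | 0.46 | 8% |
| 10:3 | 0.54π | 65% | 15 | 0.75 | 21% |

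The adjusted test stays at 5% in every row. If order was assigned by simple randomization, a split of 9:4 or worse has probability 2 × 1093/8192 = 27%, and 10:3 or worse 2 × 378/8192 = 9%.

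**Carry-over.** Suppose a share λ of the epinephrine effect persists into a later saline period. On raw values the planned contrast is 1 − fλ of the truth, with f = 6/13 or 7/13. For λ = 25% this is 87–88%, and for λ = 50% it is 73–77%. The sequence-adjusted contrast is 1 − λ/2, which is 87.5% and 75%. Adjustment therefore leaves this bias essentially unchanged. A formal between-sequence carry-over test on 7 against 6 children has about 5% to 17% power for carry-over of 50% to 100% of the effect, assuming a within-child correlation of 0.3 to 0.7.

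**The case against.** The strongest reply is that nothing in the document shows any drift. Each tooth has a baseline immediately before its pellets. If the comparison is of changes from that baseline, a stable shift in level cancels. Without drift, adjustment costs power, and at 9:4 or 10:3 the cost is not trivial. At 0.25 SD with a favorable sign the gain at 7:6 is nil. At 7:6 the planned test is conservative, so it does not inflate false positives. This is also a 13-child pilot.

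Much of that stands: the loss of precision is conditional. But the plan does not say that changes are compared, and a baseline does not remove a period difference in the response itself. A conservative test is no safeguard when the hoped-for answer is no change, and with a lopsided split the test is no longer conservative under a large drift.

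A reader might go further and infer that saline readings taken after an epinephrine tooth are contaminated, or that adjusting for sequence would cure this. The document supports neither. No interval is stated, so residual effect is possible. However, the order of steps implies that the second tooth was prepared between placements, and the INTRODUCTION argues that systemic absorption is low. A stable residual would cancel in change from the second baseline; one still fading would not, and would bias that contrast the opposite way from raw values. Nor is absence of carry-over established: the low-absorption argument is relative to injection, and the INTRODUCTION says that well-designed trials of these effects on gingival tissue in children are lacking.

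**Conclusion.** The concern holds as a conditional weakness of the analysis. The trial randomizes sequence and then analyzes as though it had not. Under a period effect of 0.5 to 1 SD at an assumed 7:6 split, the planned comparison loses between about 3 and 40 points of power against the adjusted one (76% against 79% at best, 39% against 79% at worst). At 9:4 or 10:3 the main risk shifts to bias and, at 1 SD, to a type I error above 5%. These sizes rest on assumed drift and an assumed split, with n = 13 derived from the recruitment figures. It is not shown that precision was in fact lost or that any saline reading was affected by earlier epinephrine. Adjusting for sequence also does nothing about treatment being tied to side of the mouth, since control was always on the right.

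**What to change.** Make the epinephrine-saline comparison of HR, SBP, DBP and MAP a paired analysis adjusted for randomized sequence: average the two sequence-specific mean differences, using the pooled within-sequence variance on 11 df. Apply it to change from each tooth's own pre-pellet baseline, and state that choice. Report the number of children in each sequence.

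For carry-over, report descriptively, with confidence intervals, the second-tooth pre-pellet baselines by sequence and the treatment effect by sequence. Give the actual time between the two placements. Do not rely on a formal carry-over test at n = 13, and do not read a null result as evidence that there was none.

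The reanalysis uses the recorded readings and the randomization list; the time between placements can be reported to the extent it was recorded. It needs no new patients and no change in care. The price is one degree of freedom and the no-drift power loss tabulated above, which grows as the sequences become less equal.

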Topical epinephrine has been used widely in medicine and dentistry to achieve rapid hemostasis. Studies by Korkmaz et al and Gunaratane et al showed no significant hypertensive episodes and no hemodynamic parameter changes associated with placement of 1:1000 topical epinephrine. However, others have reported topical epinephrine sensitivity on only small portion of patients. These studies showed that topical epinephrine may induce significant hemodynamic changes in only a subset of patients which included the ones with preexisting cardiovascular diseases.

A literature review of prior studies investigating the effects of topical racemic epinephrine showed its effectiveness to decrease intraoperative bleeding. Degerliyurt K. et al. showed practical use of topical epinephrine without safety concerns for sinus surgery. Vickers et al. studied the cardiovascular effects of topical epinephrine pellets and 20% ferric sulfate in endodontic surgery. They found that neither agent had any statistically significant cardiovascular effects. However, subjectively, epinephrine pellets showed better hemostasis outcome than 20% ferric sulfate.

Complications associated with use of topical epinephrine are extremely rare, and changes in cardiovascular outcomes have not been shown to be statistically significant. To the best of our knowledge, no well-designed clinical trials have been conducted to assess the cardiovascular effects of topical epinephrine on gingival tissue in a pediatric population.

The overarching purpose of this split-mouth randomized pilot study was to determine the efficacy and safety of receiving treatment with topical racemic epinephrine compared to placebo, measured by cardiovascular and hemostasis outcomes. Specifically, the primary objective of this

study was to determine if the use of racemic epinephrine has any effect on heart rate, blood pressure, or cardiac rhythm in children receiving dental care under general anesthesia. We hypothesized that the use of topical racemic epinephrine would be associated with no significant change on heart rate, blood pressure, or mean arterial pressure in children receiving dental care under general anesthesia compared to patients receiving a placebo.

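### Tables 1 and 2 test cardiovascular change without a control, and the between-side comparison that has one is neither named primary nor defined on change from baseline

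*Combined protocol and SAP*

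**What the plan says.** All of this is in the combined protocol and SAP.

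- **Baseline (METHODS, study procedures).** "After preparation, an appropriately sized zirconia crown was fit, and baseline heart rate and blood pressure were recorded". A later paragraph places the readings "immediately before pellet placement (baseline) and again at 1, 2, 3, 4 and 5 minutes after placement". The interval between the end of crown fitting and the baseline reading is not stated.
- **Application.** "Next, two saline or intervention pellets were stretched and applied directly around the gingival tissue of the prepared tooth covering the tooth circumference". Pellets were held for one "minute with gauze pressure based on manufacturer's recommendation", and residual coagulum was then removed. This is written for both kinds of pellet.
- **Pressure as a stimulus.** "To reduce pressure stimulation, no dental isolation (e.g. rubber dam) was used during any of the study procedures".
- **Within-side tests (METHODS, final paragraph).** A paired t-test and a one-way repeated ANOVA "were used for comparison of cardiovascular outcomes within controls (Table 1) and within interventions (Table 2".
- **Between-side test (same paragraph).** "A paired t-test with equal variance was used for comparing control and intervention cardiovascular values as well as time to hemostasis adequacy (Table 3". The significance level is 0.05 throughout, and none of the three tables is named as primary.
- **Hypothesis (INTRODUCTION).** No significant change in heart rate or blood pressure "in children receiving dental care under general anesthesia compared to patients receiving a placebo".

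**The concern.** The level of stimulation changes over the same minutes as the drug exposure. Preparation and crown fitting come before the baseline. A minute of gauze pressure and then coagulum removal come after it. By leaving out the rubber dam, the plan itself treats pressure as something to keep out of the study procedures. Heart rate and blood pressure could therefore move between baseline and minute 5 on either tooth with no drug involved.

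A test within the epinephrine side has nothing to set that movement against. If values settle after baseline, a real rise is offset and Table 2 shows no change, which is the hypothesised answer. If gauze pressure raises values, Table 2 shows a rise that is not due to the drug. Setting a significant result on one side beside a non-significant one on the other does not help, because that is not a test of the difference between sides. At stake is whether the primary cardiovascular conclusion rests on a controlled comparison.

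**Working it through.** The documents give no sample size calculation, SD or effect size, so there is no planned figure to reproduce. The check is the algebra of the two comparisons, followed by an illustration on assumed values.

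**1. What each comparison estimates.** Let *e* be the epinephrine effect and *d* the non-drug movement from baseline, assumed equal on the two sides.

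- Within epinephrine side (Table 2): *e* + *d*
- Within saline side (Table 1): *d*
- Between-side difference in change: (*e* + *d*) − *d* = *e*

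The Table 2 quantity is zero when *d* = −*e*, and nonzero with no drug effect whenever *d* ≠ 0. I read Tables 1 and 2 as tests of movement from the pre-pellet baseline, which is the natural reading, though the text does not spell it out.

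**2. Inputs for the illustration.**

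- From METHODS: 16 approached − 3 excluded gives n = 13. Alpha is 0.05, taken as two-sided because sidedness is not stated.
- Assumed: true rise *e* = 8 bpm; SD of change 5, 8 or 12 bpm; shared drift *d* = 0, −4, −8 or +4 bpm; correlation between the two sides' changes r = 0 or 0.5.

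**3. Formulas.** Power comes from the noncentral t on 12 degrees of freedom.

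- Within-side noncentrality: (*e* + *d*)/SD × √13. For SD 8 and *d* = −4 this is (4/8) × 3.606 = 1.80, giving power 0.38.
- Between-side: the mean is *e* and the SD is SD × √(2(1 − r)). For SD 8 and r = 0 this is 11.3, so the noncentrality is (8/11.3) × 3.606 = 2.55, giving power 0.65.

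**4. Probability of declaring a rise when *e* = 8 bpm.**

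| SD | Table 2 test, *d* = 0 | *d* = −4 | *d* = −8 | Between-side change, any shared *d* (r = 0 to 0.5) |
|---|---|---|---|---|
| 5 | 1.00 | 0.75 | 0.025 | 0.96 to 1.00 |
| 8 | 0.91 | 0.38 | 0.025 | 0.65 to 0.91 |
| 12 | 0.60 | 0.20 | 0.025 | 0.35 to 0.60 |

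**5. The opposite error.** With *e* = 0 and *d* = +4 bpm, the Table 2 test declares a false rise with probability 0.75, 0.38 or 0.20 for SD 5, 8 or 12. The two-sided error of the between-side contrast stays at 0.05.

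**6. Significance on one side only.** Take *e* = 0, *d* = +4 and SD 8, with the two sides independent. The chance that the epinephrine side alone shows a significant rise is 0.382 × (1 − 0.382) = 0.24. For exactly one side, either one, it is 2 × 0.24 = 0.47 after rounding. There is no drug effect in this example.

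**7. Values or changes in Table 3.** Suppose baselines differ by *p* between the first and second tooth treated. A comparison of raw post-pellet values carries +*p* or −*p* in each child's difference, depending on order. If *k* of the 13 children receive epinephrine second, the mean carries *p*(2*k* − 13)/13. This cannot be exactly zero, because 13 is odd; a 7:6 split leaves *p*/13. Randomised order removes *p* in expectation, but the ± *p* still adds to the spread. Change from baseline, or adjustment for baseline with an order term, addresses it directly.

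**The case against.** The strongest reply is that the design already deals with this. The saline tooth goes through the same preparation, fitting, pellet placement and gauze pressure. Each child is their own control, order is randomised, the hypothesis is set against placebo, and the matching paired test is planned as Table 3. Shared drift cancels there on average, even if raw values are compared. The plan never says that the conclusion rests on Table 2 or that the two sides' p-values are to be contrasted. Table 1 in fact displays the no-drug movement. All of this stands.

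It rules out a stronger reading that a reader might infer: that the timing of the baseline hides a real epinephrine rise in this trial. The controlled comparison hides nothing by this route. Three related inferences also fail:

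- The text does not say that baseline was taken straight after drilling. Crown fitting comes in between, and no interval is given either way.
- No vital signs are reported that show settling. Drift could be up, down or negligible under this anaesthetic, so no net bias is established.
- The baseline itself need not be redesigned. A reading just before the pellet is a reasonable reference point. Waiting for repeated readings could let bleeding stop before the pellet is applied, which would affect the hemostasis objective, and the gauze pressure would still fall after baseline.

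The reply leaves the specification open. Three sets of tests address the primary objective at the same threshold, two of them have no control, and the plan neither says which decides nor whether Table 3 uses values or changes.

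**Conclusion.** The point holds as one about analysis specification, of minor to moderate weight. Tables 1 and 2 cannot answer the placebo-referenced hypothesis, whether their results are significant or not. Table 3 can, as far as shared drift is concerned, but the plan does not give it that role or define its outcome as change from baseline.

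The power figures rest on an assumed rise, SDs, drifts and correlations. They show how far an uncontrolled test can be misled, not that it was. If there were no drift, the Table 2 test would have power equal to or above that of the between-side contrast (0.91 against 0.65 to 0.91 at SD 8). Protection against drift therefore has a price. The cancellation also assumes that drift is the same on both teeth. Freedom from shared drift does not make Table 3 sensitive: at SD 12 its power for 8 bpm is only 0.35 to 0.60, so a non-significant result there would still not show that there is no effect.

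**What to change.** - Name one primary cardiovascular analysis: the within-child difference between sides in change from the pre-pellet baseline, or a baseline-adjusted equivalent, with a term for treatment order. State which minute or summary of minutes 1 to 5 it uses, and report the estimate with a confidence interval.
- Report Tables 1 and 2 as descriptive means and SDs by minute. Use no p-value from them for the conclusion, and do not contrast significance on one side with its absence on the other.
- State the interval between the end of crown fitting and the baseline reading, or say that it was not recorded.

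This uses readings already collected, so the cost is rewording and a short reanalysis. There are two limitations to disclose. If baseline and later readings correlate weakly, simple change scores add noise, and the baseline-adjusted form is then preferable; the choice should be made without regard to the results. If an effect from the first tooth lasts into the second tooth's baseline, the change on the second tooth is distorted, and an order term does not fully remove that. The documents do not state the time between the two teeth, so it should be reported.

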The secondary objective of this study was to determine if the use of racemic epinephrine has any effect on hemostasis, as measured subjectively by the dentist performing the procedure. We hypothesized that the use of topical racemic epinephrine would reduce clotting time around the gingival tissue, resulting in more rapid hemostasis.

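### As described, the control pellet differs from the epinephrine pellet in preparation as well as in drug, so the secondary hemostasis result cannot be attributed to epinephrine alone

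*Combined protocol and SAP*

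**What the plan says.** The Introduction gives the overall aim as the "efficacy and safety of receiving treatment with topical racemic epinephrine compared to placebo". The secondary objective is to "determine if the use of racemic epinephrine has any effect on hemostasis, as measured subjectively by the dentist performing the procedure", and the hypothesis credits the drug: "We hypothesized that the use of topical racemic epinephrine would reduce clotting time around the gingival tissue, resulting in more rapid hemostasis".

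The Methods describe the pellets in one contrasting sentence: "Control pellets were prepared by soaking in 0.9% sodium chloride (physiological saline) whereas intervention pellets were obtained directly from the manufacturer". That sentence continues by giving the active pellet's content, "containing an average of 0.55 mg (0.42 to 0.68 mg/pellet) of racemic epinephrine hydrochloride per pellet". The carrier material and moisture state of the active pellet are not given, and the base material of the control pellet is not named.

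The rest of the application is common to both sides: "two saline or intervention pellets were stretched and applied directly around the gingival tissue of the prepared tooth", then held for one "minute with gauze pressure based on manufacturer's recommendation". The step for clearing coagulum after removal (suction or damp gauze) carries no restriction to one side. Hemostasis is scored at baseline and at 1, 2, 3, 4 and 5 minutes. It is adequate when bleeding from the gingiva has stopped and inadequate when there is "continued blow flow from gingival tissue, with blood contamination of the prepared tooth".

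**The concern.** A placebo isolates a drug effect only if it matches the active product in everything except the drug. Here one pellet has a soaking step and none is described for the other. The outcome is local and physical, and the Introduction itself accepts that gauze pressure without any drug can produce hemostasis. A difference in how much fluid a pellet brings to the site, or can take up from it, could therefore plausibly affect what the dentist sees. The pellets stay in place for one minute and the first score after placement is at 1 minute, so that score falls at about the time of pellet removal.

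At stake is how the secondary result is interpreted. If the epinephrine side reaches hemostasis sooner, the plan's wording would credit racemic epinephrine, although part of the difference might come from the carrier.

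**Working it through.** The documents state no sample size calculation, power or expected hemostasis effect, so there is no figure to reproduce. The check is mainly a comparison of the two sides.

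**Step 1: what differs and what is shared (Methods)**

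| Feature | Control tooth | Epinephrine tooth |
|---|---|---|
| Drug | none | racemic epinephrine, mean 0.55 mg per pellet |
| Preparation | soaked in 0.9% saline | from the manufacturer; no wetting described |
| Carrier material | not stated | not stated |
| Number, stretching, placement | two pellets, same | two pellets, same |
| Pressure | one minute, gauze | one minute, gauze |
| Clearing of coagulum | suction or damp gauze | suction or damp gauze |

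Two rows are known or described to differ (drug and preparation), and one cannot be checked (material).

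**Step 2: can the analysis separate them?** Let τ be the drug effect and κ the effect of carrier preparation on the within-patient difference. Every epinephrine tooth has one preparation and every control tooth the other, so the expected difference is τ + κ. That is one equation with two unknowns. Pairing removes differences between patients and randomized sequence balances order, but neither touches κ. The paired t-test on time and McNemar's exact test both estimate or test the sum.

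**Step 3: illustration of what κ could do to the binary test.** These are assumptions, not document figures.

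- Pairs: 16 approached − 3 excluded = 13.
- Test: exact McNemar, two-sided assumed, significant if p < 0.05. With m discordant pairs all in one direction, p = 2 × 0.5^m. For m = 5, p = 0.0625; for m = 6, p = 0.031.
- Assume no drug effect (τ = 0), independence within pairs, control adequacy a, and adequacy a + d on the epinephrine side from the carrier alone.
- Discordant probabilities: (a + d)(1 − a) in favour of epinephrine and a(1 − a − d) in favour of control. Summing trinomial probabilities over all significant tables gives:

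| Carrier shift d | a = 30% | a = 50% |
|---|---|---|
| 0 | 1.1% | 1.5% |
| 10 points | 2.6% | 2.8% |
| 20 points | 7.5% | 7.5% |
| 30 points | 17.6% | 18.0% |
| 40 points | 34.1% | 38.1% |

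The table shows only that a large carrier effect could produce a significant result without any drug effect, while a small one would rarely do so. It does not show that any shift exists. A shift in the opposite direction would hide a drug effect instead.

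**The case against.** The strongest reply is that the mismatch is partly inferred. The Methods give the active pellet's source and drug content, not its moisture. They do not say that it was dry or that its material differed from the control's. This stands: the supportable statement is that no wetting and no matching are described.

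A reader might go further and infer that a dry, absorbent active pellet was set against a wet control, so that the bias favours epinephrine. The documents do not support that, for three reasons:

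- There are no absorbency data, so neither size nor direction can be settled.
- The definition of inadequate requires bleeding from the gingiva to continue. A tooth that is merely wet or tinged with saline and blood does not meet it.
- Suction or damp gauze after pellet removal was available on both sides. It may have reduced any carried-over fluid, although it was aimed at coagulum and does not rule out a carrier effect.

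Two further inferences also fail. The 6-versus-5 threshold of McNemar's test does not measure the harm of a one-minute delay. If the test concerns reaching adequacy at any scoring point, such a delay creates a discordant pair only when it pushes a tooth past the last score at 5 minutes. Nor does a visible difference between pellets add an unmasking problem, since the Methods already state that the dentist and study personnel were unblinded.

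It is also fair to say that this is a pilot, that hemostasis is secondary, that recruitment has ended, and that product versus saline pellet is a legitimate practical question. These limit the weight of the point. They do not justify attributing the result to epinephrine alone.

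**Conclusion.** The point holds for the secondary hemostasis objective. On the text as written, carrier preparation is fully aliased with treatment, and the contrast is epinephrine pellet as supplied versus saline-soaked pellet. It is not a test of racemic epinephrine against a true placebo, and no analysis of these data can make it one.

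The size and direction of any carrier effect cannot be determined from the documents; it could favour the epinephrine side. The conclusion assumes that the active pellets were used as supplied, which is inferred from the absence of a wetting step. If they were in fact matched to the controls in material and moisture, the Methods omit this, and stating it would settle the point. The primary cardiovascular objective is not affected.

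**What to change.** For any further trial, use as control an unmedicated pellet of the same size and material, in the same moisture state as the epinephrine pellet and handled identically, so that only the drug differs.

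For data already collected with soaked controls:

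- State in the Methods the carrier material and moisture state of both pellets at application.
- Report the hemostasis result as epinephrine pellet as supplied versus saline-soaked pellet.
- Do not attribute the difference to epinephrine alone, and do not call the comparator a placebo for this outcome unless matching can be confirmed.

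The cost is a change of control pellet in future work and a few sentences of text now, with no extra patients, staff or procedures. The downside is that the hemostasis difference may turn out smaller with a matched control, and the conclusion from the present data becomes narrower.
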